I (investigator) also confirm that I will make the findings of the study publicly available through publication or other dissemination tools without any unnecessary delay and that an honest, accurate and transparent account of the study will be given. Any deviations from the study as planned in this protocol will be explained and reported accordingly.

Chief Investigator:

Signature: ..

..... **Date..15/1/2026**

Print Name (in full): [name]

Position: Professor of Urology

On behalf of the Study Sponsor:

Signature:

..... **Date.16./01./2026**

Print Name (in full):[name].....

Position:Research Governance Manager.....

STUDY SUMMARY

Identifiers	
IRAS Number:	ID: 364428
REC Reference No.:	TBC
Sponsor Reference No.:	EDGE 199328
Other research reference number(s):	UCL Data Protection number: No Z6364106/2025/10/66
Full (Scientific) title:	A study to evaluate the performance of en-face fluorescence confocal microscopy (LaserSAFE) for margin analysis during radical prostatectomy.
Short title:	The LaserSAFE study
Health condition(s) or problem(s) studied:	Prostate cancer.
Study Type:	Prospective cohort clinical trial.
Aim(s):	The main aim is to investigate the ability of the LaserSAFE technique to detect positive margins during radical prostatectomy compared to final paraffin analysis
Objectives:	
Primary objective
 
 To establish the sensitivity of pathology led LaserSAFE image interpretation to guide nerve-sparing decisions during radical prostatectomy 
Secondary objectives
 
 To evaluate the accuracy metrics of pathology led LaserSAFE image interpretation against FFPE To establish the optimal cut-off criteria to suggest a secondary resection should be performed based on LaserSAFE results To describe the prevalence of PSM in the cohort To evaluate the rate of PCa recurrence within 12 months of surgery To evaluate the urinary incontinence and erectile function scores of patients at 3 and 12 months after surgery using the EPIC-26 questionnaire
Type of trial:	Prospective cohort non-randomised clinical trial in patients diagnosed with localised prostate cancer.

Trial design and methods:	
This trial will be a multi-site, prospective, non-randomised cohort study. Participants will undergo a robotic assisted radical prostatectomy with bilateral intrafascial nerve-sparing. The LaserSAFE technique will be used to analyse the posterolateral surfaces of the prostate. In cases where a PSM is found which fulfils the criteria for secondary resection this will be carried out by the operating surgeon before the end of the procedure. All samples will be processed using standard FFPE that will act as the reference standard. Patients will be monitored according to the standard of care at each centre. Quality of life questionnaires will be collected at before surgery, at 3 and 12 months after surgery. An adaptive design will allow monitoring of accuracy metrics thought the trial and adjust secondary resection criteria to maximise nerve-sparing.

Trial duration per participant:	12 months.
Key Study milestones:	
Submission for REC and HRA approval: December 2025
 
Acquire REC and HRA approval: TBC
 
Commence recruitment at primary site: TBC
 
Open secondary sites: TBC
 
Proposed completion: TBC

Estimated total trial duration:	60 months
Planned trial sites:	
Multisite study
 
UCLH

Total number of participants planned:	693 patients
Main inclusion/exclusion criteria:	
Inclusion criteria:
 
 • Patients diagnosed with clinically significant operable cT2-T3a NO M0 PC. • Medically fit to undergo RARP. • Scheduled for robot-assisted RARP with a recommendation against intrafascial nerve sparing on at least 1 side based on multidisciplinary meetings informed by MRI, biopsy result and clinical factors. • Ability to read English sufficiently to understand PIS and able to give informed consent. 
Exclusion criteria:
 
 • Patients who received neo-adjuvant ADT.

	
 • MRI informed very low likelihood for extra prostatic extension in the proximity of NVB (Based on EPE Likert 1 score or tumour away from the posterolateral areas of the prostate) • MRI informed high likelihood for extra prostatic extension in the proximity of NVB (based on Likert 5 score or bulging tumour on MRI T2 images) • Patients in whom preoperative imaging shows rectal involvement or seminal vesicle invasion in which nerve-sparing is deemed not feasible due to oncological safety concerns. • Patients who received previous treatment for prostate cancer: External beam radiotherapy, brachytherapy, focal therapy, chemotherapy.
Statistical methodology and analysis:	
Statistical analysis
 
The primary analysis will evaluate the sensitivity of LaserSAFE to diagnose positive surgical margins per side against the final paraffin analysis. Specificity and positive and negative predictive values will be reported. Measures of accuracy will be presented with 95% confidence intervals. A definitive protocol for statistical analysis will be finalised before recruitment is finished.

Funding & Other	
Funding:	UCLH Charity Number 7298
Other support:	SamanTree Medical SA
Key Study Contacts TBD	
Committees	TMG
Sub-contractors	None

KEY ROLES AND RESPONSIBILITIES

SPONSOR: The sponsor is responsible for ensuring before a study begins that arrangements are in place for the research team to access resources and support to deliver the research as proposed and allocate responsibilities for the management, monitoring and reporting of the research. The Sponsor also must be satisfied there is agreement on appropriate arrangements to record, report and review significant developments as the research proceeds, and approve any modifications to the design.

FUNDER: The funder is the entity that will provide the funds (financial support) for the conduction of the study. Funders are expected to provide assistance to any enquiry, audit or investigation related to the funded work.

CHIEF INVESTIGATOR (CI): The person who takes overall responsibility for the design, conduct and reporting of a study. If the study involves researchers at more than once site, the CI takes on the primary responsibility whether he/she is an investigator at any particular site.

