9.3. Sample Size Calculation

The sample size was calculated to estimate the sensitivity of the LaserSAFE technique with a 95% confidence interval and a precision of $\pm 5\%$. Assuming an expected sensitivity of 91% and a positive margin prevalence of 20%, at least 126 disease-positive participants are required. This corresponds to a total of 630 participants. Allowing for up to 10% missing or non-evaluable data, the adjusted target sample size is 693 participants.

The assumptions for sample size calculations were based on the results of our previous studies where LaserSAFE demonstrated in blinded analysis of a small cohort of patients a sensitivity of 91% to detect positive margins.

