9.6.2. Primary outcome analysis

The primary analysis will evaluate the sensitivity of LaserSAFE interpretation for detecting positive surgical margins greater than 3 mm in the posterolateral prostate, using FFPE histopathology as the reference standard.

Interim analyses of sensitivity will be conducted after recruitment of the first 50, 150, 300, and 500 participants. If the observed sensitivity falls below % at any interim analysis, the trial will be stopped for futility. The final analysis will be undertaken once the target sample size of 693 participants has been reached. Sensitivity will be reported with a two-sided 95% confidence interval, calculated using the Wilson score method. Indeterminate or missing LaserSAFE results will be considered non-diagnostic and classified as false negatives in the primary analysis.

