9.6.3. Secondary Outcome Analysis

1. Diagnostic accuracy metrics. Sensitivity, specificity, positive predictive value (PPV), and negative predictive value (NPV) of LaserSAFE image interpretation will be calculated with corresponding two-sided 95% confidence intervals. These will be reported in two ways:
 - a. For detection of any positive surgical margin (PSM), regardless of length, compared with FFPE analysis.
 - b. For detection of PSMs greater than 3 mm, compared with FFPE analysis.
Two-sided 95% confidence intervals will be calculated using the Wilson score method.
2. Descriptive outcomes. The following will be summarised using descriptive statistics (means, proportions, and 95% confidence intervals as appropriate):
 - a. Rate of residual prostate cancer in secondary resections of the neurovascular bundle.
 - b. Prevalence of PSMs detected by paraffin analysis in the overall cohort.
 - c. Prevalence of biochemical recurrence or salvage treatment for prostate cancer within 12 months post-surgery.
 - d. Mean scores for the EPIC-26 urinary incontinence and erectile function domains at baseline, 3 months, and 12 months post-surgery.

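### The primary sensitivity analysis is per side in the Study Summary but sized on participants, with no stated unit or side-matching rule in 9.1 and 9.6.2 and an interval method that ignores paired sides

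*Protocol*

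**What the plan says.** The statistical methodology row of the Study Summary defines the primary analysis as the "sensitivity of LaserSAFE to diagnose positive surgical margins per side against the final paraffin analysis". It is the only place that names a unit of analysis.

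Section 9.6.2 describes the same analysis as "sensitivity of LaserSAFE interpretation for detecting positive surgical margins greater than 3 mm in the posterolateral prostate", with no unit; 9.1 is equally silent. Section 9.3 works in participants: "Assuming an expected sensitivity of 91% and a positive margin prevalence of 20%, at least 126 disease-positive participants are required", and then "This corresponds to a total of 630 participants". It does not say whether the 20% is a share of participants or of sides.

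On intervals, 9.6.2 states "Sensitivity will be reported with a two-sided 95% confidence interval, calculated using the Wilson score method", and 9.6.3 says of the secondary accuracy measures "Two-sided 95% confidence intervals will be calculated using the Wilson score method". Neither mentions that one participant supplies two sides.

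Section 6.3.1.2 has both posterolateral surfaces imaged and ties secondary resection to the bundle on the side of the positive margin. Section 6.4.1 says that presence or absence of a positive margin on FFPE will be documented and does not mention its side, although the form itself may capture it.

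**The concern.** Sensitivity per side and sensitivity per participant are different quantities, and the protocol commits to one in the summary and to the other in the sample size. Each reading has its own weakness.

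- **Participant as unit, no side match.** A man with a missed left margin and a false call on the right is positive on both tests and would be scored a true positive. The estimate is then too favourable for a technique whose result is acted on side by side. Sections 3.3 and 9.1 compare observed sensitivity with 85% at looks that have few positives.
- **Side as unit.** Each participant contributes two results that may be correlated. A Wilson interval on the raw count of sides treats them as independent and claims more precision than the data hold.

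**Working it through.** **1. The plan's own figure.** Inputs from 9.3: sensitivity 0.91, half-width 0.05, 95% confidence, prevalence 0.20, 10% allowance.

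- n = 1.96² × 0.91 × 0.09 / 0.05² = 125.85, rounded up to 126
- 126 / 0.20 = 630
- 630 × 1.10 = 693

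All three reproduce, with one independent unit per participant.

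**2. The unit of the 20%.** If it is per side, 630 participants give 630 × 2 × 0.20 = 252 positive sides and a half-width of 1.96 × √(0.91 × 0.09 / 252) = 3.5 points before clustering. On that reading, 126 positive sides need only 126 / 0.20 / 2 = 315 participants. The stated precision cannot be interpreted until the unit is known.

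**3. Participant as unit, no side match.** For a participant positive on one side, with same-side sensitivity s and false-positive rate f on the other side (f is not in the protocol and is assumed), apparent sensitivity = 1 − (1 − s)(1 − f).

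| s | f = 5% | f = 10% | f = 15% |
|---|---|---|---|
| 91% | 91.5% | 91.9% | 92.4% |
| 85% | 85.8% | 86.5% | 87.3% |
| 80% | 81.0% | 82.0% | 83.0% |

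At the 150-participant look, 20% gives 30 positives. One wrong-side credit moves 25/30 (83.3%) to 26/30 (86.7%), across 85%. At 50 participants there are 10 positives, and one credit moves 80% to 90%. With s = 85% and f = 10%, the expected number of such credits among 30 positives is 30 × 0.15 × 0.10 = 0.45, so this matters only when the count sits at the limit.

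**4. Side as unit: sensitivity.** Let b be the share of positive participants who are positive on both sides, and r the within-participant correlation. Both are assumed. Positive sides = 126(1 + b); design effect = 1 + 2br/(1 + b).

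- b = 10%, r = 0.2: 1.036, standard error +2%
- b = 15%, r = 0.5: 1.13, standard error +6%
- b = 30%, r = 0.8: 1.37, standard error +17%, the extreme of the range tried

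Wilson half-widths, unclustered against effective sample size: 4.83 and 5.05 points (b = 10%, r = 0.5); 4.62 and 5.00 (b = 20%, r = 0.5); 4.43 and 5.21 (b = 30%, r = 0.8). Wilson on 126 independent positives gives 5.07.

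Simulated coverage of the unclustered interval (40,000 runs per setting):

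| b | r = 0 | r = 0.5 | r = 0.8 |
|---|---|---|---|
| 10% | 96.4% | 95.4% | 95.1% |
| 20% | 95.5% | 93.7% | 92.6% |
| 30% | 94.4% | 91.8% | 89.9% |

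**5. Side as unit: sample size.** Reading the 20% as per participant, the total before the allowance is 126 × design effect (rounded up), divided by (1 + b), divided by 0.20. Over b = 5–30% and r = 0.2–0.8 it runs from 531 (138 / 1.3 / 0.2) to 667 (160 / 1.2 / 0.2), on both sides of 630.

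**6. Side as unit: specificity and NPV.** Most participants contribute two negative sides, so the design effect approaches 1 + r. Coverage of a nominal 95% interval is about 2Φ(1.96/√(1 + r)) − 1: 93.8%, 92.6% and 91.4% for r = 0.1, 0.2 and 0.3. With about 1,120 negative sides (630 × 2 less about 140 positive) and an assumed specificity of 90%, the half-width is 1.96 × √(0.09/1120) = 1.76 points. Multiplied by √(1 + r), it becomes 1.84, 1.92 and 2.00. The loss is about 0.1 to 0.25 points.

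**The case against.** The fair case on the other side is that the side is the only analysis unit the protocol names, and that silence in 9.1 and 9.6.2 contradicts nothing. No section says that a wrong-side call would be credited, images are annotated by side (6.3.1.3), and planning is by side (6.1.1). Clustering is commonly left to the SAP, and Wilson on an effective sample size is still a Wilson interval. The intervals drive no decision: the 85% review uses the point estimate, and the cut-off rule uses residual-tumour prevalence.

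Much of this stands, and it limits the point. Three stronger readings are tempting, and the documents do not support them.

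- **That both harms occur together.** They cannot. Wrong-side credit needs the participant as unit; narrow intervals need the side.
- **That the intervals are certainly too narrow.** This depends on a positive within-participant correlation and, for sensitivity, on a share of bilateral positives. The protocol gives neither. At 10% bilateral positives, coverage stays at or above 95%.
- **That 693 is too few.** Step 5 spans both sides of 630, and a per-side prevalence of 20% would make 630 generous.

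What does not stand is deferral of the unit itself. A SAP can add a clustering method, but it cannot follow both the summary and 9.3. The summary also lets the definitive analysis plan wait until shortly before recruitment ends, so looks against 85% could be made with the unit and matching rule still open.

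**Conclusion.** The conflict of units is in the text and does not depend on any assumption: per side in the Study Summary, participants in 9.3, no unit or matching rule in 9.1 and 9.6.2, and no unit for the 20%.

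The size of the effect does rest on assumptions and is modest. On the participant reading it is 0.9 points at 91% and 1.5 points at 85%, for a 10% false-positive rate and one positive side. That could decide an early look when the count is close to the limit. On the side reading it is a standard error for sensitivity about 2% to 6% too small with 10–15% bilateral positives, and coverage for specificity of about 93.8% to 91.4% for correlations of 0.1 to 0.3, with a similar effect for NPV. The point should be corrected because it changes what is reported and is cheap to settle before data are seen. It gives no ground for changing enrolment.

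**What to change.** - State in 9.1, 9.3, 9.6.2 and 9.6.3 that the unit of analysis is the side, as the summary already has it, and that a true positive requires LaserSAFE and FFPE to be positive on the same side. Say in 6.4.1 that the side of an FFPE-positive margin is recorded.
- Say in 9.3 whether the 20% is per side or per participant, and restate the expected number of positive sides and the resulting precision. Leave enrolment unchanged.
- For per-side measures, specify an interval that accounts for two sides per participant, for example Wilson on the effective sample size or a logistic GEE with robust variance.
- Settle the unit and the matching rule before the first look at sensitivity.
- Add the limit of more than 3 mm to the summary row so that it matches 3.3, 9.1 and 9.6.2. This is wording alignment only.

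The cost is an edit to the text, one recorded item if the form lacks it, and slightly wider intervals.

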1. INTRODUCTION

1.1. Study summary

Prostate cancer is the most common solid cancer affecting male patients worldwide. When diagnosed early, it can usually be cured with surgery (radical prostatectomy). However, this procedure can be associated with side effects such as urinary incontinence and decrease or loss of erectile function. To reduce the risk of these side effects, surgeons can preserve the nerve bundles that surround the posterolateral aspect of the prostate. However, if the tumour is extending beyond the prostate (extra-prostatic extension) close to these nerves, sparing them increases the risk of leaving cancer cells behind (positive margins). Although small positive margins appear to not be of risk to patients, larger positive margins are associated with cancer recurrence and the need for additional treatment.

Combining clinical, prostate biopsy information and magnetic resonance imaging (MRI) is the current standard method to pre-operatively predict the extent of the tumour and plan the degree of nerve-sparing deemed safe. However, these methods are poor predictors of extra-prostatic extension, resulting in many patients not being offered nerve-sparing when this could have been a safe option, placing them at risk of poor functional outcomes.

To overcome this challenge a technique called NeuroSAFE was developed in Germany. It involves taking samples of tissue from the surface of the prostate adjacent to the peri prostatic nerves, to perform a frozen section (FS) analysis. A pathologist then examines these FS samples for the presence of cancer cells at the edge of the prostate. If NeuroSAFE is positive, the surgeon can remove the corresponding nerve-bundle during the same operation to achieve a negative margin (secondary resection). This technique allows more patients to be eligible for nerve-sparing. Our group has published the results of a phase 3 randomised controlled trial which confirmed that guiding nerve-sparing decisions with NeuroSAFE can improve patient reported erectile and urinary continence outcomes. However, performing NeuroSAFE is not possible in many centres across the UK and the world. This is because it requires an expert team of pathologist and 2 technicians and is both time and resource intensive.

An alternative technique called fluorescence confocal microscopy (FCM), can be used to examine the surface of tissues to produce digital images with cellular level detail. It is much more straightforward to perform than NeuroSAFE and requires less time and resources. Furthermore, the microscope can be placed in the operating room, eliminating the need to transport samples from the operating room to the pathology laboratory. We have developed a standardised FCM technique to evaluate the posterolateral aspect of prostatectomy specimens, which we have called LaserSAFE. We recently completed and reported a feasibility study where the accuracy outcomes of LaserSAFE appear equivalent to NeuroSAFE. However, before this technique is incorporated in clinical practice, a study evaluating its clinical impact when used to guide nerve-sparing decisions is necessary.

We aim to evaluate the accuracy of LaserSAFE to detect positive margins, and define the best cut-off point to tolerate small positive margins which may bear no clinical risk to patients while maximising the potential for nerve sparing and maintaining oncological safety. Patients with localised prostate cancer undergoing radical prostatectomy will undergo bilateral nerve-sparing, the prostate specimen will be analysed using LaserSAFE and the result will inform the need for secondary resection. A pathologists will then review the final paraffin embedded specimens for the presence of positive margins. At pre-specified intervals we will evaluate the accuracy metrics of LaserSAFE against final pathology results to monitor its safety. Additionally, the length of positive margin that triggers a secondary resection will be evaluated at pre-specified intervals. This will determine the best

threshold to guide nerve-sparing decisions using LaserSAFE. If proven to be accurate and safe, the LaserSAFE technique will help expand access to nerve-sparing to many patients across the world.

1.2. Lay Summary

Prostate cancer is the most common cancer in men. If it is found early, it can often be cured with surgery to remove the prostate (radical prostatectomy). However, this surgery can cause side effects such as urine leakage (incontinence) and problems with erections. To reduce these risks, surgeons try to preserve the delicate nerves that run alongside the prostate. Unfortunately, if the cancer has spread just beyond the prostate, sparing these nerves can increase the chance of leaving cancer behind.

Currently, doctors use scans and biopsy results to decide whether it is safe to spare the nerves, but these methods are not very accurate. This means many men miss out on nerve-sparing when it could have been safe, leading to worse quality of life.

A technique called NeuroSAFE was developed to improve these decisions. During surgery, samples from the edge of the prostate are checked under the microscope. If cancer is seen, the surgeon can remove the nearby nerves straight away. By enabling more patients to receive nerve-sparing safely, NeuroSAFE has been shown to improve both early urinary control and sexual function. However, it is complex, time-consuming, and requires a large specialist team, making it hard to use in many hospitals.

A new approach called LaserSAFE may overcome these problems. It uses a type of microscope (fluorescence confocal microscopy) that produces detailed images of tissue directly in the operating room, without the need for a full pathology team. Our early research has shown that LaserSAFE can be as accurate as NeuroSAFE.

This study will evaluate LaserSAFE further to confirm how well it detects cancer at the prostate edge and to find the best “cut-off” point for when a small amount of cancer may be safe to leave, while still protecting patients from cancer recurrence. If successful, LaserSAFE could make nerve-sparing surgery safer and more widely available, helping men keep both cancer control and quality of life after surgery.

